RESULTS: From June 2018 to mid-October 2019, a total of 831 of 1179 screened patients underwent randomization. The baseline characteristics of the patients were balanced between the groups. The median follow-up was 20.9 months. (177)Lu-PSMA-617 plus standard care significantly prolonged, as compared with standard care, both imaging-based progression-free survival (median, 8.7 vs. 3.4 months; hazard ratio for progression or death, 0.40; 99.2% confidence interval [CI], 0.29 to 0.57; $P<0.001$) and overall survival (median, 15.3 vs. 11.3 months; hazard ratio for death, 0.62; 95% CI, 0.52 to 0.74; $P<0.001$). All the key secondary end points significantly favored (177)Lu-PSMA-617. The incidence of adverse events of grade 3 or above was higher with (177)Lu-PSMA-617 than without (52.7% vs. 38.0%), but quality of life was not adversely affected.

CONCLUSIONS: Radioligand therapy with (177)Lu-PSMA-617 prolonged imaging-based progression-free survival and overall survival when added to standard care in patients with advanced PSMA-positive metastatic castration-resistant prostate cancer. (Funded by Endocyte, a Novartis company; VISION ClinicalTrials.gov number, NCT03511664.).

Study Rationale

This trial is designed to overcome a clinical access issue that would otherwise block patients from reimbursement of a new cancer therapy, and therefore block or significantly delay their care.

On March 23, 2022, the FDA approved PSMA-targeted radionuclide therapy for the treatment of adult patients with prostate-specific membrane antigen (PSMA)-positive metastatic castration-resistant prostate cancer (mCRPC) who have been treated with an androgen receptor pathway inhibitor (ARPI) and taxane-based chemotherapy. PSMA-targeted radionuclide therapy is also known as ¹⁷⁷Lu-PSMA-617, Lutetium Lu 177 Vipivotide Tetraxetan, and Pluvicto™.

The FDA approval of PSMA-targeted radionuclide therapy was based on the phase III VISION trial (Sartor, de Bono et al. 2021). In the VISION trial, a specific form of PSMA-targeted PET radiotracer was used to evaluate if patients had PSMA-positive prostate cancer prior to PSMA-targeted radionuclide therapy. The specific form of PSMA-targeted PET radiotracer used in the VISION trial was ⁶⁸Ga-PSMA-11, also known as Gallium Ga 68 gozetotide. ⁶⁸Ga-PSMA-11 for the VISION trial was produced with a chemistry kit that was FDA approved on March 23, 2022, now known as Locametz™.

The FDA approval of PSMA-targeted radionuclide therapy specifies to “select patients for treatment using Locametz® or an approved PSMA-11 imaging agent based on PSMA expression in tumors”. This FDA language was a surprise, as the medical community expected to be able to use any FDA approved PSMA-targeted PET radiotracer for patient selection for PSMA-targeted radionuclide therapy, and not be restricted to ⁶⁸Ga-PSMA-11.

Mayo and many other hospitals, imaging centers and clinical practices have an active PSMA-targeted PET imaging practice using ¹⁸F-PSMA-DCFPyL PET radiotracer. ¹⁸F-PSMA-DCFPyL was FDA approved on May 27, 2021. ¹⁸F-PSMA-DCFPyL is also known as, PyL, piflufolastat F 18, and Pylarify™. ¹⁸F-PSMA-DCFPyL is more widely available than the more recently FDA-approved ⁶⁸Ga-PSMA-11. Thus, most medical centers began a PSMA-targeted PET practice with ¹⁸F-PSMA-DCFPyL, and few have established access to ⁶⁸Ga-PSMA-11.

Most patients who have undergone PSMA-targeted PET scans (PET/CT or PET/MR) are likely to have received a ¹⁸F-PSMA-DCFPyL PET scan. However, the FDA-approval for PSMA-targeted radionuclide therapy specifies that ⁶⁸Ga-PSMA-11 PET be used prior to PSMA-targeted radionuclide therapy.

In order to obtain reimbursement for and open access to PSMA-targeted radionuclide therapy for appropriate Mayo patients suffering from prostate cancer this issue has to be resolved. While Mayo and others seek clarification from Medicare on this issue, many Mayo patients would be waiting and suffering.

Therefore, we are establishing a protocol, by which we will allow for a limited number of appropriate patients to obtain a ⁶⁸Ga-PSMA-11 PET/CT scan. The ⁶⁸Ga-PSMA-11 PET/CT scan would be available even if the patient had a recent ¹⁸F-PSMA-DCFPyL PET scan (PET/CT or PET/MR). The ⁶⁸Ga-PSMA-11 PET/CT scans will be performed at Mayo Clinic in Rochester at the expense of the Mayo Clinic Rochester Nuclear Medicine Division of the Department of Radiology. The radiotracer, scan, interpretation, study coordinator time and other related costs to run the protocol will be covered without expense to the patient.

The ⁶⁸Ga-PSMA-11 radiotracer will be produced at Mayo Clinic in Rochester under an active IND (IND 151346). This study has been submitted for FDA review as an extension under the

same IND.

We recognize a patient may, as a result of this protocol, get two PSMA-targeted PET/CT exams within a short period of time. This will result in a small amount of additional radiation. However, without this scan and extra radiation, there could be a significant delay in access to cancer therapy, a therapy which may be life extending. It should be recognized that the PSMA-targeted radionuclide therapy the patient is planning to undergo results in a significantly higher radiation exposure than the additional PSMA-targeted PET/CT scan included in this trial.

We intend to make the 68Ga-PSMA-11 PET/CT imaging and interpretation of that imaging available in the electronic record for patients and their care team, so they can guide clinical care decisions.

We anticipate referrals for 68Ga-PSMA-11 PET/CT under this protocol to come from Urology, Medical Oncology, Radiation Oncology, and Radiology. We anticipate performing up to six 68Ga-PSMA-11 PET/CT scans per day. We anticipate this trial will run for up to 12 months. Therefore, the total population of patients we plan to scan with 68Ga-PSMA-11 PET/CT is not expected to exceed 250.

It is possible we may need to extend this trial and increase the enrollment depending on the timing of the anticipated resolution of the Medicare and Insurance limitations on coverage described above. Alternatively, when our ability to produce an FDA approved version of 68Ga-PSMA-11 allows us to convert our clinical practice away from 18F-PSMA-DCFPyL this protocol will no longer be needed. That practice conversion is currently under active development and is dependent in part on completion of construction of new PET radiochemistry facilities in Charlton North.

Given that production of 68Ga-PSMA-11 is limited at our site, we may need to modulate access to patients in part depending on radiotracer and scanner availability. We also have limitations in terms of access to PET/CT. Thus, we will perform the majority of, or all of these 68Ga-PSMA-11 PET/CT exams within the research facilities of the PET Imaging Resource on Charlton 6.

Primary Endpoint: Safety

Measurement: Monitoring of patients for self-reported unexpected adverse reactions from the time of injection until the time they leave the care of the Division of Nuclear Medicine. If any adverse reactions are reported, the patient will be evaluated by a nurse and/or physician and will receive appropriate care. The PI or those designated by the PI will ascertain the severity of the adverse event and how likely the adverse reaction was associated with the injected 68Ga-PSMA-11.

To date we have seen no adverse reactions to IV administered 68Ga-PSMA-11 at Mayo Clinic in Rochester and we have administered over 400 doses.

68Ga-PSMA-11 Administration

The injected dose will be 185 MBq (5 mCi) (range 111-259 MBq; 3-7 mCi) of 68Ga-PSMA-11. PET imaging will begin 50-100 minutes after injection. A use of existing Central/PICC lines is considered acceptable for 68Ga-PSMA-11 administration.

We may repeat a 68Ga-PSMA-11 injection and PET/CT in either of the following circumstances:

- The patient had an unavoidable delay in care (such as a motor vehicle accident) and there is evidence or clinical concern that the patient's cancer significantly progressed or responded to therapy in a way that could affect management of his cancer.
- The patient still meets the criteria for enrollment in the study and 3 months of time or more has elapsed since the last 68Ga-PSMA-11 injection.

68Ga-PSMA-11 PET/CT protocol

The established 68Ga-PSMA-11 PET/CT imaging protocol will be followed. The scans will be performed on the Siemens VISION 600 PET/CT or GE DMI PET/CT on Charlton 6. The CT will be performed without IV or oral contrast and will follow standard clinical PET/CT protocol parameters. The exams will cover the orbits to thighs, unless otherwise specified by the Radiologist/Nuclear Medicine physician protociling the specific exam for a given patient.

Patient selection for enrollment

Inclusion Criteria. All the following criteria must be met.

- An adult male patient who...
 - o is actively under the care of a Medical Oncology, Radiation Oncology or Urology physician at Mayo Clinic.
 - o is deemed eligible (or potentially/likely eligible) for PSMA-targeted radionuclide therapy by a Nuclear Medicine Physician or Radiologist in the Nuclear Medicine therapy practice, or by the Prostate Theranostic Tumor Board (PTuB)
 - eligibility will be documented in the medical record by the clinical practice
 - it is acceptable for the patient to be eligible for PSMA-targeted radionuclide therapy in all regards except for having completed a PSMA-targeted PET scan showing PSMA-positive prostate cancer
 - It is acceptable for a patient to be potentially eligible for therapy, but have a relative contraindication, such as a minor laboratory abnormality, and be on the list for discussion at the PTuB in the future
 - o has not received a 68Ga-PSMA-11 PET/CT or PET/MR, or for whom a repeat 68Ga-PSMA-11 PET/CT exam is needed per the clinical practice to ensure eligibility
 - o does not otherwise have access to a reimbursable clinical 68Ga-PSMA-11 PET scan
 - o An adult above the ages of 18

Exclusion criteria. Any of the following.

- A patient who is:

- unable to consent per Mayo guidelines
- unable to lay still, or otherwise successfully complete the imaging exam

Study procedures

Patients who meet all inclusion and no exclusion criteria will be invited to participate in the study. The study coordinator will set up an appointment with the subject to discuss the study, answer any relevant questions, and obtain informed consent. The study coordinator will schedule the 68Ga-PSMA-11 PET/CT scan. Patient's participation in the study will end once their imaging visit is complete. The 68Ga-PSMA-11 PET/CT scans will be clinically interpreted with the report and imaging available in the patient's medical record.

Radiation Dose Estimate for CT Component of PET/CT

The effective dose for a trunk CT (orbits to mid-thigh) is 6.3 mSv for males. The effective dose for a 7 mCi IV injection of 68Ga-PSMA-11 is 4.4mSv.

Adverse Event (AE) Monitoring and Reporting

The site principal investigator is responsible for reporting any/all serious adverse events to the IRB and IND sponsor as described within the protocol, regardless of attribution to study agent or treatment procedure.

The sponsor/sponsor-investigator is responsible for notifying FDA and all participating investigators in a written safety report of any suspected adverse reaction that is both serious and unexpected.

Definitions:

Adverse Event: Any untoward medical occurrence associated with the use of a drug in humans, whether or not considered drug related.

Note: An adverse event (also referred to as an adverse experience) can be any unfavorable and unintended sign (e.g., an abnormal laboratory finding), symptom, or disease temporally associated with the use of a drug, without any judgment about causality. An adverse event can arise from any use of the drug (e.g., off-label use, use in combination with another drug) and from any route of administration, formulation, or dose, including an overdose.

Suspected Adverse Reaction: Any adverse event for which there is a reasonable possibility that the drug caused the adverse event.

Note: For purposes of IND safety reporting, “**reasonable possibility**” means there is evidence to suggest a causal relationship between the drug and the adverse event. A suspected adverse reaction implies a lesser degree of certainty about causality than adverse reaction, defined below.

Unexpected: An adverse event or suspected adverse reaction is considered “unexpected” if

- It is not listed in the investigator brochure or.
- Is not listed at the specificity or severity that has been observed; or,
- If an investigator brochure is not required or available, is not consistent with the risk information described in the general investigational plan (protocol) or elsewhere in the current IND application (as amended).

Serious (previously SAE): An adverse event or suspected adverse reaction is considered “serious” if, in the view of either the investigator or sponsor, it results in any of the following outcomes:

- Death,
- A life-threatening adverse event,
- Inpatient hospitalization or (Prolongation of existing hospitalization), or
- A persistent or significant incapacity or substantial disruption of the ability to conduct normal life functions, or a congenital anomaly/birth defect.

Note: Important medical events that may not result in death, be life-threatening, or require hospitalization may be considered serious when, based upon appropriate medical judgment, they may jeopardize the patient or subject and may require medical or surgical intervention to prevent one of the outcomes listed in this definition.

Life-Threatening: An adverse event or suspected adverse reaction is considered “life-threatening” if, in the view of either the investigator or sponsor, its occurrence places the patient or subject at immediate risk of death.

Note: It does not include an adverse event or suspected adverse reaction that, had it occurred in a more severe form, might have caused death.

Attribution to agent or procedure:

When assessing whether an adverse event (AE) is related to a medical agent(s) medical or procedure, the following attribution categories are utilized:

- Definite - The AE is clearly related to the agent(s)/procedure.
- Probable - The AE is likely related to the agent(s)/procedure.
- Possible - The AE may be related to the agent(s)/procedure.
- Unlikely - The AE is doubtfully related to the agent(s)/procedure.
- Unrelated - The AE is clearly NOT related to the agent(s)/procedure.

FDA REPORTING REQUIREMENTS FOR SERIOUS ADVERSE EVENTS (21 CFR Part 312)

NOTE: Investigators **MUST** immediately report to the sponsor **ANY** Serious Adverse Events, whether or not they are considered related to the investigational agent(s)/intervention (21 CFR 312.64)

An adverse event is considered serious if it results in **ANY** of the following outcomes:

- 1) Death
- 2) A life-threatening adverse event
- 3) An adverse event that results in inpatient hospitalization or prolongation of existing hospitalization for ≥ 24 hours
- 4) A persistent or significant incapacity or substantial disruption of the ability to conduct normal life functions

5) A congenital anomaly/birth defect.

6) Important Medical Events (IME) that may not result in death, be life threatening, or require hospitalization may be considered serious when, based upon medical judgment, they may jeopardize the patient or subject and may require medical or surgical intervention to prevent one of the outcomes listed in this definition. (FDA, 21 CFR 312.32; ICH E2A and ICH E6).

ALL SERIOUS adverse events that meet the above criteria **MUST** be immediately reported to the sponsor within the timeframes detailed in the table below.

Hospitalization	Grade 1 Timeframes	Grade 2 Timeframes	Grade 3 Timeframes	Grade 4 & 5 Timeframes
Resulting in Hospitalization ≥24 hrs	7 Calendar Days			24-Hour 3 Calendar Days
Not resulting in Hospitalization ≥24 hrs	Not required		7 Calendar Days	

Expedited AE reporting timelines are defined as:

- “24-Hour; 3 Calendar Days” - The AE must initially be reported within 24 hours of learning of the AE, followed by a complete expedited report within 3 calendar days of the initial 24-hour report.
- “7 Calendar Days” - A complete expedited report on the AE must be submitted within 7 calendar days of learning of the AE.

¹Serious adverse events that occur more than 30 days after the last administration of investigational agent/intervention and have an attribution of possible, probable, or definite require reporting as follows:

Expedited 24-hour notification followed by complete report within 3 calendar days for:

- All Grade 4, and Grade 5 AEs

Expedited 7 calendar day reports for:

- Grade 2 adverse events resulting in hospitalization or prolongation of hospitalization
- Grade 3 adverse events

² For studies using PET or SPECT IND agents, the AE reporting period is limited to 10 radioactive half-lives, rounded UP to the nearest whole day, after the agent/intervention was last administered. Footnote “1” above applies after this reporting period.

Confidentiality

Information about study subjects will be kept confidential and managed according to the requirements of the Health Insurance Portability and Accountability Act of 1996 (HIPAA). Those regulations require a signed subject authorization informing the subject of the following:

- What protected health information (PHI) will be collected from subjects in this study
- Who will have access to that information and why
- Who will use or disclose that information
- The rights of a research subject to revoke their authorization for use of their PHI.

In the event that a subject revokes authorization to collect or use PHI, the investigator, by regulation, retains the ability to use all information collected prior to the revocation of subject authorization.

Source Documents

The Source data comprise all information, original records of clinical findings, observations, or other activities in a clinical treatment necessary for the reconstruction and evaluation of the treatment response. Source data are contained in source documents. Examples of these original documents, and data records include: hospital records, clinical and office charts, laboratory notes, radiological imaging data, memoranda, subjects' diaries or evaluation checklists, pharmacy dispensing records, recorded data from automated instruments, copies or transcriptions certified after verification as being accurate and complete, microfiches, photographic negatives, microfilm or magnetic media, subject files, and records kept at the pharmacy, at the laboratories, and at medico-technical departments involved in the study.

Records Retention

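### Does an IND-made tracer undercut an access rationale built on label text that asks for an approved PSMA-11 agent?

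*Protocol*

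**What the plan says.** The Study Rationale opens with the purpose: "This trial is designed to overcome a clinical access issue that would otherwise block patients from reimbursement of a new cancer therapy". It then quotes the therapy label, which tells clinicians to select patients with Locametz "or an approved PSMA-11 imaging agent based on PSMA expression in tumors". Two paragraphs later, when comparing this tracer with the more widely used ¹⁸F-PSMA-DCFPyL, it says the approval "specifies that ⁶⁸Ga-PSMA-11 PET be used prior to PSMA-targeted radionuclide therapy". The word *approved* is absent there.

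On the study product, the same section states that the "radiotracer will be produced at Mayo Clinic in Rochester under an active IND (IND 151346"). An approved product from the site lies in the future: the protocol will no longer be needed "when our ability to produce an FDA approved version of 68Ga-PSMA-11 allows us to convert our clinical practice" away from the other tracer.

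The extra radiation is justified by access: "without this scan and extra radiation, there could be a significant delay in access to cancer therapy". The one endpoint given is "Primary Endpoint: Safety", measured through self-reported reactions until the patient leaves the Division's care. Under Study procedures, participation ends with the imaging visit.

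**The concern.** The chain of reasoning seems to break at one word. If therapy selection requires an approved agent, a scan with an investigational product does not meet that condition as written, and the paraphrase hides the gap by treating any ⁶⁸Ga-PSMA-11 scan as sufficient. The benefit set against a further injection and CT would then be assumed rather than established, including for patients who have recently had an ¹⁸F-PSMA-DCFPyL scan.

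The design also appears unable to expose the problem. A study whose declared purpose is access collects nothing on coverage, therapy started or time to therapy. If payers declined the scan, the study would finish with a clean safety result and no record that its purpose had failed.

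**Working it through.** The point turns mainly on wording, so the statements are set side by side. Only the radiation figure needs arithmetic.

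**1. Is the wording inconsistent?** Yes, within the Study Rationale. The label quotation carries *approved*; the later restatement does not. The restatement has a narrower job, though: the sentences around it contrast two tracers and explain why a patient already scanned with one may need the other. The full label condition stands a few lines above it.

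**2. Is the status of the study product hidden?** No. The same section gives the IND number, says the study was submitted for FDA review as an extension of that IND, and treats an approved version as a later step.

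**3. Does it follow that the scan fails to open access?** The argument needs three premises:
- (a) the quoted label names Locametz or an approved PSMA-11 agent: stated;
- (b) the study tracer is made under an IND: stated;
- (c) payers, or the therapy practice, will not accept a scan with that product: not stated anywhere.

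Without (c), the share of scanned patients authorised for therapy has no anchor and could be 0% to 100%. The protocol says clarification is being sought from Medicare and describes the coverage limits as unresolved. Its own claim is hedged: it says delay could occur without the scan, not that the scan guarantees therapy.

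**4. What is the cost per scan?** Inputs are from the radiation dose section: 6.3 mSv for the trunk CT and 4.4 mSv for a 7 mCi injection.
- At 7 mCi, the top of the stated range: 6.3 + 4.4 = 10.7 mSv.
- At the stated 5 mCi, assuming effective dose scales linearly with activity: 4.4 × 5/7 = 3.1 mSv, so 6.3 + 3.1 = 9.4 mSv.

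The protocol plans for no more than 250 patients and notes that the therapy itself gives a much larger exposure.

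**5. Is the scan a duplicate for everyone?** No. The inclusion criteria admit patients who meet every therapy requirement except a completed PSMA PET scan. No proportion with a recent ¹⁸F-PSMA-DCFPyL scan among enrolled patients is given, so the number of duplicates cannot be computed. Every scan is clinically read and placed in the medical record to guide care, so it has a use beyond authorisation.

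**6. Would any repair change what the study does or concludes?**
- *Restoring the word.* Eligibility, procedures, endpoint and enrolment limit all stay the same. Only background text moves.
- *A payer check before scheduling.* While Medicare's position is open, this could hold back or exclude the very patients the study serves.
- *Counting authorisations.* The protocol states no aim of estimating them. The decisions fall after participation ends, so the end-of-participation text would have to change, and possibly the HIPAA authorization, which must say what information is collected. The count would show how often therapy was authorised, not how much sooner than without the scan, and it would leave the safety result as it is.

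**The case for a change.** The best case for a change rests on the mismatch between purpose and measurement. The protocol does not describe itself mainly as a tracer safety study; it says it exists to remove an access block, and it uses access to justify extra radiation. It also foresees extending the study and enrolling more patients, depending on how coverage develops, while collecting nothing on whether its own scans helped. A separate analysis plan could not supply this, because data that are not collected cannot be analysed. One item abstracted from the chart would be cheap next to the scan itself.

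Part of this stands. The protocol never says why a scan with the IND product should satisfy the label wording it quotes, and one sentence doing so would be a courtesy to the reader. A descriptive count could also interest the site when it considers an extension. What does not stand is the step from *not measured* to *defective*. The stated endpoint is safety, the planned monitoring addresses it, and no stated hypothesis, estimate or decision rule depends on an authorisation rate. The extension is tied to outside events (resolution of coverage, readiness of an approved product), not to study data.

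**Conclusion.** No change to the plan is called for. The paraphrase is looser than the label text quoted above it, which is a slip in background wording with every relevant fact disclosed in the same section. The absence of an access outcome is a design choice consistent with a study that provides a scan and monitors its safety.

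The possible harm cannot be sized from the document. The radiation side is bounded at 10.7 mSv per scan (9.4 mSv at 5 mCi under linear scaling), but the access side is unconstrained between 0% and 100%. The conclusion assumes that the document's silence on payer refusal is not evidence of refusal, and that access is the motive for the study rather than a quantity it undertook to estimate. Evidence that payers do not accept IND-made scans for selection would reopen the justification for the extra scan, but that evidence lies outside this protocol.

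### Is the projection of 250 patients unsound because it does not follow from six scans a day over 12 months and leaves repeat scans uncounted?

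*Protocol*

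**What the plan says.** The Protocol's Study Rationale sets out the expected workload in three consecutive statements: "We anticipate performing up to six 68Ga-PSMA-11 PET/CT scans per day"; "We anticipate this trial will run for up to 12 months"; and "Therefore, the total population of patients we plan to scan with 68Ga-PSMA-11 PET/CT is not expected to exceed 250". It then adds that enrolment may have to be increased, that on-site tracer production and PET/CT access are limited, and that access may have to be rationed. The same section defends the extra radiation by comparing the planned radionuclide therapy with "the additional PSMA-targeted PET/CT scan included in this trial", in the singular.

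68Ga-PSMA-11 Administration opens the door to more than one scan: "We may repeat a 68Ga-PSMA-11 injection and PET/CT in either of the following circumstances". The first circumstance is an unavoidable delay in care with concern that the disease has changed. The second is that the patient still qualifies for enrolment and "3 months of time or more has elapsed since the last 68Ga-PSMA-11 injection". Neither carries a maximum number, and the first has no minimum interval.

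Patient selection for enrollment admits a man who has had no 68Ga-PSMA-11 scan, or one who needs a repeat in the view of the clinical practice. Study procedures then says that "participation in the study will end once their imaging visit is complete". The radiation section gives 6.3 mSv for the CT and adds: "The effective dose for a 7 mCi IV injection of 68Ga-PSMA-11 is 4.4mSv".

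**The concern.** The word introducing the 250 makes it read as the product of a daily rate and a duration, and it is not that product. The unit also changes, because the inputs count scans and the output counts patients. That is harmless only if each patient has one scan, and the repeat rule says otherwise.

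The primary endpoint is safety, observed from each injection, so the number of injections is the natural measure of exposure. If 250 does not limit injections, a reader cannot tell from it how much tracer the study may administer, or how much radiation one participant may receive. Ending participation after the imaging visit also appears to leave no room for a repeat three months later. If these points affected a safety conclusion or hid an inconsistency in the sample size, the text would need correcting.

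**Working it through.** **Step 1: try to reproduce 250.** The inputs are six scans a day and 12 months, both ceilings, from Study Rationale. The number of scanning days is not stated, so it is assumed. Scans = scans per day × scanning days.

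| Assumed scanning days | Scans |
|---|---|
| 240 to 260 working days | 6 × 240 = 1,440 to 6 × 260 = 1,560 |
| one day a week, 52 weeks | 6 × 52 = 312 |
| one day a week, 50 weeks | 6 × 50 = 300 |
| 2, 3 or 4 days a month | 144, 216 or 288 |
| one day a week, 42 weeks | 6 × 42 = 252 |

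The two ceilings alone do not give 250. Only an added assumption, such as 42 full scanning days, comes close.

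**Step 2: check whether 250 conflicts with the ceilings.** 250 / 6 = 41.7 full days; 250 / 52 = 4.8 scans a week; 250 / 1,560 = 16% of weekday capacity. An expected total below capacity is consistent with limits stated as "up to" values and with the restricted tracer and scanner access described in the same section. The figure is unexplained but not contradicted.

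**Step 3: radiation.** One visit at the top of the activity range is 6.3 + 4.4 = 10.7 mSv. At the planned 5 mCi, scaling the tracer dose in proportion to activity (an assumption), it is 6.3 + 4.4 × 5/7 = 9.4 mSv. Two visits at 7 mCi give 21.4 mSv. Visits at months 0, 3, 6 and 9 give 4 × 10.7 = 42.8 mSv; counting a fifth at month 12 gives 53.5 mSv. Each total is a multiple of the stated figures, which are labelled per CT and per injection and are not presented as a limit per participant.

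**Step 4: injections.** If every patient had four, the total would be 250 × 4 = 1,000. For all four to fall within 12 months at three-month spacing, each of the 250 men would need his first scan by month 3 and would have to qualify again three times. If 10% to 20% had one repeat (assumed), the total would be 250 × 1.1 = 275 to 250 × 1.2 = 300.

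**Step 5: effect on the safety endpoint.** The protocol makes no precision claim. As an illustration only, with no reactions seen, the one-sided 95% upper limit for the reaction rate is 1 − 0.05^(1/n). For n = 250 this is 1.2%; for n = 300 it is 1.0%, treating repeat injections in one man as independent. The choice of unit hardly matters at plausible repeat rates.

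**Step 6: set the sections side by side.** The three-month route requires that enrolment criteria still be met. For a man already scanned, that means the criterion that a repeat is needed, together with continuing actual or potential eligibility for therapy and no reimbursable scan elsewhere. The eligibility text therefore anticipates repeats. It also allows the end-of-participation sentence to be read as closing one visit, with a later repeat tested again against the criteria. The protocol does not say whether this is what is meant.

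**The case for a change.** The strongest case for acting is that safety is observed per injection, and the protocol itself reports earlier experience as more than 400 doses rather than as patients. A projection in patients is therefore the wrong unit for exposure. The radiation defence speaks of one scan, and the comparison with therapy cannot be tested for several scans because no therapy dose is given. The delay-in-care route neither refers back to the enrolment criteria nor sets an interval, so the restraint found for the three-month route does not clearly apply to it. Clarifying all this would take only two or three sentences.

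Much of that is accurate. 250 does not bound injections, no maximum is stated, and the sections on administration and procedures leave open whether a repeat belongs to the same participation. But 250 is explicitly a number of patients, so the unit is not in doubt. The singular scan sits in a discussion of having two PSMA-targeted scans close together and does not state a maximum per patient. What participants are told about repeats, cumulative radiation or renewed consent would normally be in the consent pages, which are not available here, so their silence cannot be held against the plan. The totals of 1,000 injections and 42.8 mSv depend on a pattern of enrolment and repeated requalification that nothing in the protocol leads one to expect.

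**Conclusion.** The observation is correct but calls for no change to the plan. 250 does not follow from the two ceilings, which allow 1,440 to 1,560 scans on 240 to 260 assumed working days. It is a projection at about 16% of the upper of those totals, it is not shown to be wrong, and the protocol says it may be increased. The protocol derives no power, precision, analysis or stopping rule from it. The radiation figures come to 10.7 mSv per visit at 7 mCi and remain correct, visit by visit, if a scan is repeated.

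Two wording points remain: the connecting word before 250, and how the repeat rule in 68Ga-PSMA-11 Administration relates to the end of participation in Study procedures. The sponsor must reconcile those two sections and decide which reading applies. This is a clerical matter for the next routine amendment, and either answer leaves the safety monitoring and its reporting as they are. The conclusion assumes that repeats are occasional; the protocol gives no repeat rate.
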